## 12.6 Reporting and Exclusions

### 12.6.1 Evaluation of toxicity.

Evaluation of toxicity will be monitored throughout the study period. AE will be assessed at each study visit.

### 12.6.2 Evaluation of response.

Evaluation of response will be monitored at each visit and the presence/absence of PE will be ascertained at the completion of the study.

## 13. DATA AND SAFETY MONITORING PLAN (DSMP)

Data and Safety Monitoring Plan (DSMP) is not applicable since both the intervention arms are considered standard of care.

The data will be stored in a secure RedCap database. The only other research personnel with access to the database will be the PI ([name]) and the study coordinator ([name]). Laboratory personnel and other research personnel will not have access to identifiers.

## HUMAN SUBJECTS CONCERNS

Patients will be recruited from New York Presbyterian – Weill Cornell and Queens campuses' affiliated Obstetric Clinics and The Hypertension Center. Institutional Review Board (IRB) approval for the Weill Cornell campus will be obtained before initiation of the trial. In accordance with IRB regulations, informed consent will be obtained at the enrollment visit, prior to randomization. We do not expect more than minimal risk to our subjects since both strategies tested are part of the current standard of care. Despite the absence of evidence for increased major bleeding associated with ASA (3, 4), we will inform participants of the risk of non-major bleeding associated with ASA in pregnancy and discomfort for additional time spent at each visit for research purposes. Risk for loss of confidentiality will be discussed and minimized by storing all identifiers in a password secured Redcap database. RedCap access will be limited to necessary research personnel. Data exported for analysis will be done in a de-identified manner. The potential benefit of this study to its participants include risk reduction of PEC. Consistently with the current equipoise, this benefit is considered to be similar for both groups and not distinct from standard of care.

**NEW AND/OR UNIQUE ASSAY/TECHNOLOGY:** Not applicable.

**EXTERNAL SUPPORT/COLLABORATION/FUNDING:** We will seek the support of the Preeclampsia foundation and the American Heart Association.

## Appendix

## Validated Aspirin Adherence Questionnaire

## Simplified medication adherence questionnaire (SMAQ)

1	Do you ever forget to take your aspirin?				
	Yes	No			
2	Are you careless at times about taking your aspirin?				
	Yes	No			
3	Sometimes if you feel worse, do you stop taking your aspirin?				
	Yes	No			
4	Did you not take any of your aspirin over the past weekend?				
	Yes	No			
5	Thinking about the last week, how often have you not taken your aspirin?				
	Never	1x	2-3x	4-5x	6-7x
6	Over the past 3 months, how many days have you not taken any aspirin at all?				
	≤2 days	>2 days

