### 1.2. Secondary Objectives

- Evaluate and compare the adherence of pregnant women to 81 mg and 162 mg of daily low-dose aspirin using a validated, Simplified Medication Adherence Questionnaire (SMAQ).
- Compare maternal and fetal outcomes in pregnant women at a high risk for preeclampsia who are treated with either 81 mg or 162 mg of daily aspirin during pregnancy, including preeclampsia  $\geq$  37 weeks, severe maternal hypertension, preterm delivery, fetal growth restriction, placental abruption and maternal/fetal mortality.
- To compare the time-to-event for developing PE for women treated with 81mg vs. 162mg of aspirin per day.
- To assess the adherence to low dose aspirin in pregnant women that are a high risk for preeclampsia and compare adherence rates for women on 81mg vs 162mg of aspirin per day.

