## 5.2 Treatment groups

At the initial visit, participants will be consented then randomized using the RedCap software to either Arm 1: 81mg ASA per day or Arm 2: 162mg ASA per day.

Adherence will be ascertained by questionnaire including a validated questionnaire: the simplified medication adherence questionnaire (SMAQ) (5).

Once funding can be obtained, we may further evaluate adherence by quantifying Thromboxane metabolite excretion in the collected and stored urine samples (urine samples will be stored in our BioBank at the Nephrology lab [[name] lab, [name]]). This method has previously been used in pregnancy to determine ASA activity/adherence (13, 14).

The patients will then be monitored throughout pregnancy for side effects, study endpoints and clinical data will be collected as described in section 5.1. Delivery records and postpartum course will also be considered to rule out delivery/postpartum complications including obstetric hemorrhage and postpartum PE.

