## **6. DOSING DELAYS/DOSE MODIFICATIONS**

Patients will obtain their medications from their respective pharmacies. Women randomized to Arm 1, will be instructed to take one tablet of baby ASA 81mg per day while those in Arm 2, will be asked to simultaneously take 2 tablets per day for a total of 162mg.

Therapy will be prescribed at the baseline visit to be initiated before 16 weeks of gestation. Aspirin therapy will continue until a week prior to planned delivery or upon admission for unplanned/imminent delivery as per routine clinical care.

Aspirin is an over the counter medication and comes in very large pill containers thus rendering pill counts unpractical. Adherence will be assessed using a validated questionnaire.

Dose modifications are not planned. If for a clinical reason, the participant or their healthcare providers have a concern or issue with the randomized dose; then that participant can be taken off the study dose and, with their permission, would be observationally monitored in an intention to treat analysis.

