## **12.2 Treatment Regimens**

Arm 1: 81mg oral ASA daily.

Arm 2: 162mg oral ASA daily.

Patients will obtain their prescriptions from their respective pharmacies. Women in Arm 1, will be instructed to take one tablet of 81mg aspirin per day; those in Arm 2, will be asked to take two tablets simultaneously orally once per day. Therapy will be initiated at the baseline visit and continue until 1 week before planned delivery or upon admission for unplanned/imminent delivery as per clinical routine.

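### The SMAQ never asks how many tablets were taken, so it cannot reliably compare adherence to one versus two 81 mg tablets

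*Combined protocol and SAP*

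**What the plan says.** One secondary objective in section 1.2 contrasts the arms on "adherence of pregnant women to 81 mg and 162 mg of daily low-dose aspirin using a validated, Simplified Medication Adherence Questionnaire". Sections 6 and 12.2 define the arms by number of tablets. Arm 1 takes one 81 mg tablet daily. Women in Arm 2 "will be asked to simultaneously take 2 tablets per day for a total of 162mg" (section 6), and section 12.2 repeats that they "will be asked to take two tablets simultaneously orally once per day".

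On measurement:

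- Section 5.2: "Adherence will be ascertained by questionnaire including a validated questionnaire", namely the SMAQ. No other adherence item is given.
- Section 6: aspirin "comes in very large pill containers thus rendering pill counts unpractical", followed by "Adherence will be assessed using a validated questionnaire".
- Section 5.2, on a urine biomarker: "Once funding can be obtained, we may further evaluate adherence by quantifying Thromboxane metabolite excretion".
- The schedule in section 5.1 places the adherence questionnaire at the 18-22, 24-28 and 34-38 week visits. A separate medication list is taken at those visits, at baseline and postpartum. Section 12.1 adds medication reconciliation at each visit.
- The Appendix prints all six SMAQ items. The last asks "Over the past 3 months, how many days have you not taken any aspirin at all".
- Section 12.5 names no analysis of adherence.

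**The concern.** The objective is dose-specific, so adherence has to mean taking the assigned number of tablets. The questionnaire asks whether aspirin was forgotten, missed or stopped. Two behaviours can pass through it: regular one-tablet use in the 162 mg arm and regular two-tablet use in the 81 mg arm. Both are easy in this trial. It is open-label, the tablets are the same over-the-counter product in both arms, and women obtain them from their own pharmacies.

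At stake is how the secondary result is read. Similar SMAQ rates could be reported as 162 mg being taken as well as 81 mg when some women were taking the other arm's dose. In a dose comparison, knowledge of the dose taken also helps to interpret a null finding, a possibility that section 2.2 raises. If the count is not recorded at visits, it cannot be reliably recovered later: pill counts are ruled out and the thromboxane assay is unfunded.

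**Working it through.** **Step 1. Set the items against the dose instruction.**

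| SMAQ item | Subject | Tablet count asked? | Half dose in the 162 mg arm | Double dose in the 81 mg arm |
|---|---|---|---|---|
| 1 | Forgetting | No | May be reported, if she reads the question as her full dose | Not detected |
| 2 | Carelessness | No | May be reported | Not detected |
| 3 | Stopping when feeling worse | No | May be reported | Not detected |
| 4 | Taking none over the weekend | No | Can be answered as taken | Not detected |
| 5 | How often not taken in the last week | No | May be reported | Not detected |
| 6 | Days with no aspirin at all in 3 months | No | Counts as taken | Not detected |

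Ordinary forgetting is not the gap. Both tablets are taken together once daily, so a forgotten dose is usually a whole dose, and the SMAQ picks that up. The gap is sustained half-dosing or doubling that the woman does not report.

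**Step 2. Dose taken relative to dose assigned.** One tablet in the 162 mg arm is 81/162 = 50% of the assigned dose and equals the other arm's dose. Two tablets in the 81 mg arm is 162/81 = 200%.

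**Step 3. Size of the hidden gap, under stated assumptions.** Let A be the SMAQ-adherent proportion, assumed equal in both arms. Among SMAQ-adherent women, let a share s of the 162 mg arm take one tablet and a share t of the 81 mg arm take two. The SMAQ difference is A - A = 0. Adherence to the assigned dose is A(1-t) in the 81 mg arm and A(1-s) in the 162 mg arm, so the gap not seen is

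A(1-t) - A(1-s) = A(s-t).

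Two values of A come from the documents: 75%, the stage 1 planning figure in section 12.3 (which does not define adherence), and 100 - 46 = 54%, from the SMAQ study cited in section 2.1.1, which found up to 46% non-adherent. The shares s and t are my assumptions; the documents give nothing on them.

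| s | t | Gap at A = 75% (points) | Gap at A = 54% (points) |
|---|---|---|---|
| 5% | 0 | 3.75 | 2.7 |
| 10% | 0 | 7.5 | 5.4 |
| 20% | 0 | 15.0 | 10.8 |
| 5% | 5% | 0 | 0 |
| 10% | 5% | 3.75 | 2.7 |
| 20% | 5% | 11.25 | 8.1 |
| 5% | 10% | -3.75 | -2.7 |

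**Step 4. A yardstick.** The plan's 197 per arm (394 in total) reproduces exactly from 8.6% versus 1.5%, 85% power and two-sided 5%, with a continuity correction. With 197 per arm, two-sided 5%, 80% power and an uncorrected two-proportion z test, the detectable difference d below a rate p solves

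d = 1.96 √(2p̄(1-p̄)/197) + 0.842 √((p(1-p) + q(1-q))/197), where q = p - d and p̄ = (p+q)/2.

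- p = 75%: d = 13.1 points (13.08).
- p = 54%: d = 14.0 points (14.05).

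With t = 0, the hidden gap reaches that size when s = 13.08/75 = 17.4% or s = 14.05/54 = 26.0%. Of the 14 gaps tabulated, only one (s = 20%, t = 0, A = 75%) exceeds the yardstick.

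**The case against.** The strongest reply is that the dose may already be recorded. The medication list is its own row in the schedule, reconciliation is done at each visit, and section 5.2 leaves room for items beyond the SMAQ. The case report forms are not among the documents, so the absence of a tablets-per-day field cannot be proved. This stands as a possibility, and the fix allows for it. But nothing in the documents says that these records capture tablets actually taken, or that they enter the adherence comparison.

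Second, a woman told to take two tablets together may read the questions about her aspirin as meaning the full dose and report a dropped tablet under items 1, 2, 3 or 5. That is true of some women, which is why the conclusion is that the SMAQ cannot *reliably* show adherence to dose. The reading is uncontrolled, it does not help with item 6 and helps little with item 4, and it does nothing for doubling.

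Third, the magnitude rests on assumed shares, its sign is open, and most scenarios fall below what the trial could detect. That stands in full. The figures show what could be hidden and do not estimate a bias.

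Fourth, comparing missed aspirin with an unmodified questionnaire described as validated is defensible. It is, for that question. The stated objective, however, is adherence to two specific doses, and the documents do not say that the SMAQ was validated to tell one tablet from two.

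Finally, the lack of any adherence analysis in section 12.5 is a separate omission that would remain whatever the items asked. It matters here only because no planned analysis closes the gap.

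**Conclusion.** The concern holds. As specified, the SMAQ comparison answers whether women in the two arms miss aspirin equally often. It does not reliably answer whether they take the dose to which they were assigned. This rests on the full text of the six items and on the absence of any stated link between other medication records and the adherence comparison.

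The size is unknown. Under the assumed shares the hidden gap runs from -3.75 to 15.0 percentage points, with equal SMAQ adherence in both arms assumed. Its direction depends on which arm departs more from its assigned number of tablets. The consequence is confined to the secondary adherence objective and to the interpretation of a null result; the primary intention-to-treat comparison does not depend on the SMAQ. The change should be made because it is cheap and the information would otherwise be lost, but it does not threaten the trial's main conclusion.

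**What to change.** Leave the SMAQ and its wording as they are. At the three scheduled questionnaire visits, add one separate question asking how many 81 mg tablets the woman took on the days in the last week when she took aspirin. Report tablets per day by arm and visit. In section 12.5, state that the arms will be compared on the proportion who are SMAQ-adherent and taking the assigned number of tablets, alongside the SMAQ result itself. If the medication list or reconciliation already records tablets taken per day, say so in the protocol and use that field in place of a new question.

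The cost is one self-reported question at three existing visits and a sentence in section 12.5. The downsides are that the answer is still self-report, so a woman who conceals her dose could conceal it here too, and that there will be a second adherence result, on a composite not itself stated to be validated. The change alters no dose and no clinical rule.
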